7.2 Study population

Inclusion criteria

- Preterm neonate, born at less than 32 weeks of gestation.
- Must be on invasive mechanical ventilation due to neonatal respiratory distress syndrome.
- Informed consent signed by parent or legal guardian.

Exclusion criteria

- Any congenital malformations
- Any chromosomopathies
- Any cardiopathies
- Any neurological malformations

These criteria have been selected because all of these pathologies can affect the patient's respiratory pattern, so it is possible that newborns with these criteria may have different management necessities, more time on mechanical ventilation, or more complications related to their underlying pathology.

Withdrawal criteria

- **Request to revoke consent for the study:** the parents or legal guardians of the neonate can express voluntary decision to be excluded from the study at any point. (see Annex 6)
- **Neonates' death:** from enrolment until the end of the follow-up period.

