7.4 Variables and measurements

Independent variable

The independent variable is the **invasive mechanical ventilation protocol** used during the weaning. It is conceived as a **dichotomous qualitative nominal variable** and is expressed as PSV/ACVGV:

- PSV: Pressure support ventilation
- ACVGV: Assist control volume guarantee ventilation

Dependent variables

There are two dependent variables: **number of reintubations** and **time of weaning**.

The **number of reintubations** is the main dependent variable. It is a **discrete quantitative variable**. The higher the number of reintubations, the higher the risk of complications, so it is a good variable to determine which protocol is more effective. Extubation failure is defined as reintubation within 24-72 hours, so the number of reintubations will be counted for the first 72 hours after the extubation.

The **time of weaning** is the secondary dependent variable. It is a **continuous quantitative variable**. It is counted from the moment the weaning is started until the extubation is executed. The longer this time is, the greater the risk of complications arising from invasive ventilation that the child may have, so it is a good variable to determine which protocol is more effective.

Covariates

- **Gestational age at birth/type of preterm:** once is born, the baby will be classified into one of these categories. It is a *dichotomous qualitative ordinal variable*:
 - Extremely preterm (< 28 weeks of gestation)
 - Very preterm (28-32 weeks of gestation)
- **Birthweight:** it is a *continuous quantitative variable* measured in grams.
- **Sex:** it is a *dichotomous qualitative nominal variable*. Categorized as men or women.
- **CPR after birth:** it is a *dichotomous qualitative nominal variable*. It will be expressed as yes or no.

- **5-minute Apgar score** (see Annex 1): It is a quantitative variable, but categorized in the following intervals, resulting in a *polychotomous qualitative ordinal variable*:
 - Apgar 0-3
 - Apgar 4-6
 - Apgar 7-10
- **Risk factors of prematurity:**
 - **Previous preterm birth:** it is a *dichotomous qualitative nominal variable*. It will be expressed as yes or no.
 - **Second trimester miscarriage (> 16 weeks):** it is a *dichotomous qualitative nominal variable*. It will be expressed as yes or no.
 - **Multiple pregnancy:** it is a *dichotomous qualitative nominal variable*. It will be expressed as yes or no.

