7.6 Flow chart

7.7 Data collection

All baseline and outcome data will be collected prospectively using a data collection form. This data form has been designed to collect all clinical and procedural information (see Annex 7) from the different NICUs participating in this project.

Each patient will be identified with a special ID to maintain anonymity, the patient's name cannot appear. Once a week, the neonatologist expert or hospital coordinator of each hospital must collect all the files gathered by the neonatologists of his/her hospital and add them to an online database. When the statistical specialist analyses the database, he/she will not know the name of the baby, or the technique used.

A data quality control service will be contracted to supervise the process and ensure correct data collection.

Period 1: Inclusion and baseline data

The main investigator will contact potential participants to evaluate if they meet all the inclusion criteria and any exclusion criteria. This will take place in the NICU, when there is a preterm infant with NRDS on invasive mechanical ventilation.

If the patient meets all the study criteria, an information form (see Annex 4) and an informed consent (see Annex 5) will be given to the parents after proper explanation.

When the patient is already part of the study, the researcher will proceed with the collection of baseline data, corresponding to the covariates.

Period 2: Intervention period

A baseline researcher, not involved in the outcome assessment, will be responsible for assigning the ID code to each participant. In addition, this

researcher will distribute to the neonatologist the randomised allocation prepared by the biostatistician, indicating the protocol he/she will use.

During the intervention, the baseline researcher must ensure that all dependent variables related to the intervention are collected.

Period 3: Follow up

After 72 hours of the intervention, the baseline researcher not involved in the outcome assessment will evaluate the dependent variable (reintubation).

Once completed, the data form must be sent to the hospital coordinator or neonatologist expert who will add the data to the general online database.

Later, when all the data from all the participants is completed, it will be sent to the statistician expert for analysis.

Figure 18 - Summary of the data collection process

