- 6. Formation sessions** (April 2024): An online meeting will be held with the whole team to provide theoretical training on neonatal resuscitation and neonatal mechanical ventilation. Particular emphasis will be placed on invasive mechanical ventilation and weaning. During this meeting, a consensual and detailed document will be sent to the hospital coordinators of each centre with the values of each parameter of the ventilator necessary for both the initiation of weaning and extubation. It will also include the clinical and gasometrical criteria for weaning, extubation and reintubation.

The aim of this training is to homogenise the process and reduce differences in the results between centres.

- 7. Creation of a database** (April 2024): A computer scientist will be hired to create a database, so that the data collected before, during and after the intervention can be correctly recorded.

STAGE 3: Sample recruitment, intervention, and data collection (27 months: May 2024 – July 2026)

8. Sample recruitment: As mentioned above, a consecutive stratified sampling method of extremely and very preterm newborns with NRDS that are on invasive mechanical ventilation, admitted to the NCIU of the participating hospitals will be carried out. Each co-investigator at each centre will be responsible for enrolling patients who meet all the inclusion criteria and any of the exclusion criteria, after the parents or legal guardians have signed the informed consent form (see Annex 5). Each participant will be randomised to one of the intervention groups of the clinical trial. The hospital coordinators of each centre will supervise this process.

Recruitment will continue until each centre has recruited the number of participants assigned by the stratification, with a 1:1 ratio. This is expected to take approximately 26 months (2 years and 2 months).

9. Intervention: During this period, patients will be assigned to one of the protocols for weaning, PSV in one arm of the study and ACVGV in the other.

This process can take a few days or even a few weeks, so an extra month has been added to the projected 26 months for this stage.

10. Follow up: After the intervention, all patients enrolled in the study will be followed for the first 72 hours after extubation, as all clinical data will be recorded in the baby's medical record.

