11. Data registry: As the patients are enrolled and followed up, the researchers will record the data of each variable to be studied in the data form to be later entered into a database shared by the 5 hospitals.

This will be done by the HC or the neonatologist expert of each hospital.

Sample recruitment will take place in parallel with the intervention and follow up, as some patients will be undergoing the intervention while others are being recruited or followed up.

The newborns will be enrolled in the study while they are on invasive mechanical ventilation. Once they meet the criteria to start weaning, the intervention will start, and patients will be randomised to one of the two protocols: PSV or ACVGV. When the patient meets the criteria for extubation, the intervention is concluded, and a 72-hour follow up will begin.

While the data is registered, the data manager will be responsible for data processing, quality control and report writing for interim and final data analysis.

During this stage, three-monthly online meetings led by the principal investigator and the data manager will be held with the hospital coordinators of each participating hospital, with the aim of facilitating communication between centres, assessing compliance with deadlines, notifying problems that have occurred during this time and being able to solve them as quickly as possible.

STAGE 4: Statistical analysis and data interpretation (4 months: August – November 2026)

12. Statistical analysis (August – October 2026): During this period, statistical analysis of the data will be performed by a subcontracted statistician, who will analyse all the data collected by descriptive, bivariate, and multivariate analysis. He or she will be blinded to the study groups.

13. Results and conclusions (November 2026): The statistician will present the results to the whole research team, who will discuss the outcomes and draw conclusions.

STAGE 5: Results publication and dissemination (5 months: December 2026 – April 2027)

14. Article writing, revision, and publication (December – February 2027): The MI will write the final article with the results and conclusions. It will be edited and supervised by English correctors and published afterwards.

15. Dissemination (March – April 2027): The written study will be published as a journal article. National and international congresses will be attended to present the results.

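### Death is a withdrawal criterion but not a recorded study variable, and the interim report has no stated content, so no written step compares harm by arm

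*Combined protocol and SAP*

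**What the plan says.** All references are to the combined protocol and SAP.

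**Death.** Section 7.2 lists the infant's death as a withdrawal criterion, "from enrolment until the end of the follow-up period". Section 7.4 says "There are two dependent variables": number of reintubations and time of weaning. The primary one is tied to extubation, "so the number of reintubations will be counted for the first 72 hours after the extubation". Everything else in section 7.4 and Table 4 is the protocol variable or a baseline covariate. Under the intervention, the Annex 7 form asks for the protocol code, reintubation and weaning time.

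**Monitoring.** Section 10.3 gives Stage 3 as 27 months, of which about 26 are recruitment: "Recruitment will continue until each centre has recruited the number of participants assigned by the stratification". In that stage "the data manager will be responsible for data processing, quality control and report writing for interim and final data analysis", a duty also listed in section 10.2. Three-monthly online meetings are held "with the aim of facilitating communication between centres, assessing compliance with deadlines, notifying problems that have occurred during this time" and so that these can be solved quickly. Under section 7.7 each hospital, once a week, "must collect all the files gathered by the neonatologists of his/her hospital and add them to an online database". The statistician comes in at the end: "Later, when all the data from all the participants is completed, it will be sent to the statistician expert for analysis".

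**Safety and oversight.** Section 7.8 asserts that participation adds no risk. Section 8 contains no interim or safety analysis. Section 9 requires approval by the CEIC, cites a legal system of controls, and commits investigators to publish all results, unfavourable ones included.

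**The concern.** Two things are at stake.

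The first is bias in the primary comparison. Reintubations are counted only after extubation. An infant who dies during weaning has no primary outcome and, by section 7.2, is withdrawn. If the infants who die are those most likely to have been reintubated, an arm with more deaths can show fewer reintubations. Without deaths by arm beside the primary result, a reader cannot judge this.

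The second is safety. Both modes are in routine use, but the trial exists because nobody knows which is better, and section 7.4 itself links more reintubations to more complications. If one arm did clearly worse, the plan names no table that would show it, no person to look, and no action to follow.

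**Working it through.** **1. A death, followed through the plan**

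- Section 7.2: the infant is withdrawn.
- Section 7.4: with no extubation there is no 72-hour window, so no primary outcome. Weaning time also has no end point.
- Section 10.3, item 11: only the study's variables go onto the form, and death is not one of them.
- Annex 7: no field for death or for the reason for withdrawal.
- Sections 8.1 to 8.3: the analyses cover the two dependent variables and the covariates.

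No step therefore puts the death into the trial data or compares it by arm.

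**2. A harm signal, followed through recruitment**

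- Forms enter the database weekly (7.7), so the data exist.
- The data manager writes interim reports (10.2, 10.3). Content, timing, breakdown by arm, reader and consequence are not stated.
- The three-monthly meetings deal with communication, deadlines and problems.
- The statistician receives data only when all participants are complete, with analysis scheduled for August to October 2026.
- Sections 7.8 and 8 add no safety comparison.

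**3. The plan's own figure**

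Inputs from section 7.3.1: 16%, a difference of 0.1 (workable only as 10 percentage points), two-sided alpha 0.05, power 0.80, drop-out 5%. The arcsine formula is n = 2(1.960 + 0.842)²/h², with h = 2·asin√p₂ − 2·asin√0.16.

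- p₂ = 0.26: n = 257.1 per arm, and 257.1/0.95 = 270.6, so 271 as printed.
- p₂ = 0.06: n = 145.8 per arm, and 145.8/0.95 = 153.5, which does not match.

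The 271 therefore corresponds to 16% versus 26%. The 26% is inferred, because section 7.3.1 prints no second proportion and no direction.

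**4. Scale**

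- Reintubation: at a true 10-point difference, the worse arm has 271 × 0.10 = 27 more reintubated infants over the trial, of which 135.5 × 0.10 = 14 fall in the second half.
- Deaths: section 3.2.9 gives mortality below 10% and survival up to 98%. Applied to both arms together, 542 × 0.02 = 10.8 and 542 × 0.10 = 54.2, so about 11 to 54 deaths. This assumes that general figures for the syndrome hold for ventilated infants over the trial's own observation period, which the documents do not establish.

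**5. What a numerical pause rule would add**

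Assumed rule: eight looks, at 30, 60, 90, 120, 151, 181, 211 and 241 infants per arm, pausing if the reintubated proportions differ by more than 3 pooled standard errors (200,000 simulated trials per scenario, 271 per arm).

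| True proportions | Chance of a pause |
|---|---|
| 16% vs 16% | 1.2% |
| 16% vs 26% | 45% |
| 6% vs 16% | 75% |

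At 16% versus 26% an average of 52.0 infants per arm are not yet randomised, so at most 52.0 × 0.10 = 5.2 of the 27 excess reintubations are avoided. At 6% versus 16%, a size of benefit that the trial might hope to see from PSV, the rule would usually pause the trial. That is a real trade-off, which is why a fixed threshold is not part of the required change.

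**The case against.** The strongest defence is that the safeguards exist but are lightly written. Both modes are standard care. Every infant has a study ID and a randomised allocation, and section 10.3 says clinical data are in the medical record, so deaths by arm can be recovered. Section 9 obliges investigators to publish unfavourable events. The three-monthly meetings are led by the principal investigator with the data manager and aim at solving problems quickly. Interim reports are already assigned. The CEIC has a general oversight role. The flow chart and the consent annexes are not in the supplied text, so their treatment of withdrawals cannot be checked.

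Most of this stands, and it rules out two stronger readings. A reader might infer that deaths are lost for good and could never be compared by arm. The documents do not support that: the records, IDs and allocations would allow it. A reader might also infer that nothing could stop a harmful arm. The meetings, the interim reports and the CEIC leave room for ad hoc action.

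What the defence does not supply is a planned step. Recovering deaths depends on someone deciding to do so afterwards. A promise to publish events does not say that they are collected for every randomised infant. The meetings and reports have no defined data to examine. Clinicians see only their own centre, with quotas of 49 to 179 infants over both arms (7.3.3), so a moderate excess may show only in pooled data.

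**Conclusion.** The point holds as a gap in planning. Death has no place in the variables, the form or the analysis; infants who die before extubation leave the primary outcome; and no written step compares deaths or reintubations by arm during about 26 months of recruitment. These conclusions rest on the text alone.

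The size is uncertain. The 27 excess reintubations assume a true 10-point difference. The 11 to 54 deaths assume that section 3.2.9 applies to these infants. Larger scenarios, such as arms at 2% and 10% mortality (271 × 0.08 = 22 extra deaths) or reintubation at 31% to 36% in the worse arm, are illustrations only: nothing in the documents suggests that either ventilation mode has such effects.

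A reader might also infer that a formal stopping boundary is required. The documents do not support that for two routine modes, and the calculation above shows that the choice is debatable. The change should be made, but it does not call the design into question.

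**What to change.** 1. **Record and report death.** Add death (yes/no, date) to Annex 7 and to section 7.4. Collect it for every randomised infant to the end of the 72-hour follow-up, or up to revocation if consent is revoked. Report it by allocated arm in the final analysis, beside the primary result.
2. **Define the interim report.** In sections 7.8 and 10.3, make it a three-monthly table, by coded arm, of deaths and of infants reintubated within 72 hours among those with complete follow-up. Do not show it to treating staff, and so do not present it at the coordinators' meetings. Refer a marked imbalance to the CEIC, and settle that role with the committee at submission, because section 9 describes its part only in general terms.
3. **Protect the final test.** State in section 8 that p < 0.05 applies to the final analysis only and that no efficacy claim is made at interim.

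A numerical pause threshold is optional and for the sponsor to choose. If one is used, state the denominator, the form of the standard error and whether it is one- or two-sided.

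The cost is protocol wording, one form item and about 27/3 = 9 short tables. Data already arrive weekly, and section 11.2 budgets 300 hours for data validation and quality control, including the data manager.

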10.4 Chronogram

STAGES AND ACTIVITIES	STAF	2023				2024				2025				2026				2027																				
		S	O	N	D	J	F	M	A	M	J	J	A	S	O	N	D	J	F	M	A	M	J	J	A	S	O	N	D	J	F	M	A					
STAGE 0 – ELABORATION OF THE PROTOCOL AND STUDY DESIGN																																						
1. First session	Main investigator Study coordinator																																					
2. Bibliographic research and protocol elaboration	Main investigator																																					
3. Contact with participating hospitals	Main investigator Study coordinator																																					
STAGE 1 – ETHICAL APPROVAL																																						
4. Ethical evaluation and approval	CEIC																																					
STAGE 2 – COORDINATION AND HEALTH PROFESSIONALS TRAINING																																						
5. First meeting with the research team	Main investigator Study coordinator Hospital coordinator																																					
6. Formation sessions	Main investigator Study coordinator Hospital coordinator Co-investigator HCP																																					
7. Creation of data base	Computer scientist																																					
STAGE 3 – SAMPLE RECRUITMENT, INTERVENTION, AND DATA COLLECTION																																						
8. Sample recruitment	Hospital coordinator Co-investigator																																					
9. Intervention																																						
10. Follow-up																																						
11. Data registry	Hospital coordinator Co-investigator Data manager																																					
STAGE 4 – STATISTICAL ANALYSIS AND DATA INTERPRETATION																																						
12. Statistical analysis	Statistical specialist																																					
13. Results and conclusions	Main investigator Study coordinator Hospital coordinator																																					
STAGE 5 – RESULTS PUBLICATION AND DISSEMINATION																																						
14. Article writing, revision and publication	Main investigator																																					
15. Dissemination	Main investigator Study coordinator																																					

11. BUDGET

11.1 Not included costs

- **Staff:** The research team personnel will not receive additional remuneration for their contributions. Economic incentives for their participation are not considered appropriate, as researchers already obtain recognition and intellectual benefits from their scientific accomplishments. They are MI, SC, HC, CI, and HCP.
- **Protocols for weaning:** as they are part of the usual clinical practice, no additional costs will be generated.
- **Insurance:** it will not be taken out, as all procedures conducted in the study are part of the usual clinical practice.

11.2 Included costs

Subcontracted services

- **Data validation and quality control:** This includes the data manager. This task will be carried out by an external company, and we estimate the cost of this service at 10.500€ (35€/h for 300 hours. A calculation of approximately one hour and a half per week have been made).
- **Statistical specialist:** Will be paid 35€/h, with an estimated total of 75 hours. The estimated budget for this service is 2.625€.
- **Computer scientist:** Will be hired to create the online database. Will be paid 30€/h, with an estimated total of 10 hours. The estimated budget for this service is 300€.

TOTAL: $10.500 + 2.625 + 300 = 13.425\text{€}$

Formation costs

- **Formation sessions:** An online theoretical training on neonatal resuscitation and neonatal mechanical ventilation will be offered to all professionals. The person giving the course will be paid 35€/h and will give 1 lecture of 3 hours.

TOTAL: 105€

Travel expenses, allowances, and meals costs

- **Hospital coordinators meetings:** During the study, the main investigator and the study coordinator will have one meeting with the hospital coordinators. A budget of 100€ per person has been allocated to cover travel, accommodation, and meals. There will be a total of 7 people (the 5 hospital coordinators, the main investigator, and the study coordinator).

TOTAL: 700€

Article publication and dissemination

- **Article publication:** It has an estimated cost of 2.500€. This includes the open access publication, revision, edition, formatting, layout graphic design, and preparations of the digital metadata.
- **Linguistic correction:** Before submitting the article to the journal, a linguistic proof-reader will be required to avoid errors. The estimated cost is 300€.
- **Translator:** If there is a need to translate the study in other language as Spanish, an English translator specialized in medical language may be needed. If it was necessary, the estimated cost would be about 900€.
- **National and International congress:** We must take into consideration the payment of the inscription, travels, accommodations, and diets. Two assistants, the main investigator, and the study coordinator, will assist to both of the congresses.

The estimated cost of the national congress is 1.300€, as the registration fee is around 400 euros per person. The international congress is more expensive, so an estimation cost of 2.900€ have been done. The total budget for both congresses is about 4.200€.

TOTAL: 2.500 + 300 + 900 + 4.200 = 7.900€

TOTAL OF THE STUDY: 13.425 + 105 + 700 + 7.900 = 22.130€

Table 5 - Budget details of the study

	TYPE OF COST	UNIT COST	HOURS or UNITS	SUBTOTAL
Subcontracted services	Data validation and quality control	25€/patient	542 patients	10.500€
	Statistical specialist	35€/h	75 hours	2.625€
	Computer scientist	30€/h	10 hours	300€
	SUBTOTAL: 13.425€			
Formation	Formation sessions	35€/h	3 hours	105€
	SUBTOTAL: 105€			
Travel expenses, allowances, and meals costs	Hospital's coordinators meetings	100€/person	7 persons	700€
	SUBTOTAL: 700€			
Article publication and dissemination	Article publication	2.500€	1	2.500€
	Linguistic correction	300€	1	300€
	Translator	900€	1	900€
	National congress	1.300€	1	1.300€
	International congress	2.900€	1	2.900€
	SUBTOTAL: 7.900€			
				TOTAL: 22.130€

